### 9.2. Analysis Populations

#### 9.2.1. Safety Population

The Safety Population will consist of all subjects who have received any dose of pamrevlumab. This population is also defined as the intent-to-treat (ITT) population.

#### 9.2.2. Full Analysis Set Population

The Full Analysis Set Population (FAS) will consist of all subjects in the Safety Population who have at least one evaluable post-baseline FVC assessment.

## 9.3. Statistical Analysis

### 9.3.1. General Considerations

Descriptive summaries will be provided for all study parameters including baseline characteristics, safety, efficacy, pharmacokinetic and pharmacodynamic parameters. Continuous variables will be reported using number of subjects, mean, standard deviation or standard error, median, minimum, and maximum. In general, standard deviation is provided to describe the distribution of a parameter, such as baseline, safety, and PK/PD parameters; standard error is provided for statistical analyses of efficacy endpoints. Geometric mean will be included for PK/PD variables. Categorical variables will be reported by the frequency and percentage of subjects within each outcome category. Two-sided 95% confidence intervals will be presented for key efficacy parameters and two-sided 90% confidence intervals for PK/PD parameters. All statistical tests will be performed at  $\alpha=0.05$  level of significance, using two-sided tests, unless otherwise stated. Assessments as well as derived parameters will be presented in data listings for all subjects in the ITT/Safety Population.

Statistical consideration for the OLE are included in Section 16, Appendix 6. Detailed description of the analyses and summaries of efficacy and safety will be presented in the SAP.

### **9.3.2. Subject Enrollment and Disposition**

The number of subjects in each study population as well as subject completion status and reasons for early discontinuation will be summarized.

### **9.3.3. Demographics and Baseline Characteristics**

Subject demographics, baseline characteristics, baseline disease characteristics, and baseline efficacy measures will be summarized. Baseline disease characteristics include general medical history, disease specific characteristics, and prior treatments. Baseline efficacy measures include PFT parameters, hand and arm functions, cardiac and muscle MRI parameters, and quality of life parameters.

## **9.4. Efficacy Analyses**

Efficacy analyses will be based on the FAS population. Rules of handling missing data will be described in the Statistical Analysis Plan (SAP). Analyses based on observed data will be performed for sensitivity evaluation.

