### 2.2. Duchenne Muscular Dystrophy

Duchenne muscular dystrophy (DMD) is usually inherited in an X-linked recessive fashion, but it can occur as a result of spontaneous mutation in boys from families without a known history of the condition. On the basis of some 40 studies including several million male births, incidence at birth of Duchenne muscular dystrophy is around 1:3300, and its prevalence in the population (in terms of the total male population) is around 1:16500 ([Emery, 1991](#)).

DMD is a result of mutations (mainly deletions) in the dystrophin gene (DMD; locus Xp21.2). Mutations lead to an absence of or defect in the protein dystrophin, which results in progressive muscle degeneration with loss of independent ambulation by the age of 13 years ([Bushby, 2010](#)).

In skeletal muscles of DMD patients constant myofiber breakdown results in persistent activation of myofibroblasts and altered production of extracellular matrix (ECM) resulting in extensive fibrosis. Muscle fibrosis is the only myo-pathologic parameter that significantly correlated with poor motor outcome as assessed by quadriceps muscle strength, manual muscle testing of upper and lower limbs, and age at ambulation loss ([Desguerre, 2009](#)).

Patients with DMD are generally wheelchair bound before they develop significant respiratory muscle weakness. Respiratory complications are the primary cause of morbidity and mortality in DMD as progressive respiratory muscle weakness leads to hypoventilation and/or recurrent atelectasis and pneumonia, secondary to decreased cough effectiveness ([McKim, 2012](#)).

After age 10 to 14, patients gradually begin to lose respiratory muscle function based on pulmonary function tests (PFTs) such as forced vital capacity (FVC). The median loss in FVC (% predicted) is estimated to be 8.0% per year ([Phillips, 2001](#), [Tangsrud, 2001](#)).

Because of improvements in respiratory care, cardiac dysfunction is now a leading cause of morbidity and mortality in DMD patients ([Schram, 2013](#)). Progressive myocardial fibrosis, as detected by late gadolinium enhancement (LGE), is strongly correlated with the left ventricular ejection fraction (LVEF) decline in Duchenne muscular dystrophy patients. Longer steroid treatment duration is associated with a lower age-related increase in myocardial fibrosis burden ([Tandon, 2015](#)).

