## 9. STATISTICAL CONSIDERATIONS

### 9.1. Sample Size Determination

This study tests the hypothesis of whether pamrevlumab can attenuate the annual decline from baseline to Week 104 in FVC in non-ambulatory DMD patients. A total of 22 subjects is planned to achieve 80% power to test the null hypothesis of change in percent predicted FVC of -5% against the alternative hypothesis, assuming a mean change of -2% and standard deviation of 5% based on 2-sided one sample t-test at 0.05 significance level. The hypotheses are:

H0: change in percent predicted FVC less than or equal to -5%

Ha: change in percent predicted FVC greater than -5%.

The primary efficacy endpoint will be met if the annual change in percent predicted FVC is greater than -5% at the end of the study (lower bound of 2-sided 95% confidence interval is greater than -5%).

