### **9.4.1. Primary Endpoint**

The primary endpoint is the annual change from baseline to Week 104 in percent predicted FVC during treatment with pamrevlumab. The mean annual change in percent predicted FVC and the corresponding 2-sided 95% confidence interval will be presented. The primary efficacy endpoint will be met if the lower bound of 2-sided 95% confidence interval is greater than -5%.

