5.3. Handling of Dropouts or Missing Data

All analyses will be based on observed data; missing data will not be imputed.

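### The sensitivity analysis named for missing FVC uses observed data, so it cannot show whether the -5% criterion would survive faster decline after withdrawal

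*Protocol*

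**What the plan says.** Protocol section 9.4 bases efficacy analyses on the FAS, defers the missing-data rules to the SAP, and adds: "Analyses based on observed data will be performed for sensitivity evaluation". The FAS is limited to treated subjects "who have at least one evaluable post-baseline FVC assessment" (protocol 9.2.2). The success rule in protocol 9.4.1 is a fixed bound: "The primary efficacy endpoint will be met if the lower bound of 2-sided 95% confidence interval is greater than -5" percent.

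The supplied SAP is for the open-label extension (OLE). Its section 5.3 states: "All analyses will be based on observed data; missing data will not be imputed". Its sections 9.2.2 and 9.2.3 use all observed values after treatment discontinuation, and the only sensitivity analysis it mentions (section 5.1) concerns local laboratory values. The addendum to the main-study SAP corrects p-values, makes small reporting changes and adds immunogenicity analyses. It adds nothing on missing FVC. Version 1.0 of the main-study SAP, dated June 25, 2020 according to the addendum, is not among the supplied documents.

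**The concern.** A sensitivity analysis is useful when it varies the assumption that could overturn the result. Here that assumption is how FVC behaved in subjects who stopped being measured. An observed-data analysis does not vary it. Depending on the method, it leaves those subjects out, lets them follow the subjects still observed, or carries their own earlier decline forward. None of these tests a worse course after the last measurement.

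The design makes this direction matter. There is no control arm in which such a bias could partly cancel, so losing poor outcomes moves the estimate towards success. Protocol 2.2 describes respiratory complications as the main cause of morbidity and mortality in DMD, so loss related to lung function is plausible. Under protocol 7.1.4, efficacy testing after early withdrawal is encouraged but not required. Treated subjects with no post-baseline FVC fall outside the FAS, so no FAS analysis can count them. At stake is false reassurance about a positive result.

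**Working it through.** **1. Inputs**
- Protocol 9.1: "A total of 22 subjects is planned to achieve 80% power", to "test the null hypothesis of change in percent predicted FVC of -5" percent, "assuming a mean change of -2% and standard deviation of 5% based on 2-sided one sample t-test at 0.05 significance level".
- Success rule: lower bound of the 2-sided 95% CI above -5 (protocol 9.4.1).
- Reference decline: "The median loss in FVC (% predicted) is estimated to be 8.0% per year" (protocol 2.2).
- Assumed, because the documents give no dropout rate and protocol 9.1 makes no allowance for one: m = 1 to 5 of 22 treated subjects with no usable FVC.
- Assumed: observed subjects have mean -2 and SD 5 (the planning values). Missing subjects have mean -8 and the same SD.

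**2. The plan's own figure**

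Normal formula: n = [5 × (1.960 + 0.842) / 3]² = 21.8, rounded up to 22. The planned size is reproduced. (The exact t-test gives 76.5% power at 22. That is a side point.)

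**3. Observed-data bound, k = 22 - m subjects**

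Bound = -2 - t(0.975, k-1) × 5/√k. For m = 3, k = 19: -2 - 2.1009 × 1.1471 = **-4.41**, criterion met.

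**4. All-treated bound, same case**
- Mean = (19 × -2 + 3 × -8)/22 = -62/22 = -2.818.
- Within-group sum of squares = 18 × 25 + 2 × 25 = 500.
- Between-group sum of squares = 19 × 0.818² + 3 × 5.182² = 93.3.
- SD = √(593.3/21) = 5.315; SE = 5.315/√22 = 1.133.
- Bound = -2.818 - 2.0796 × 1.133 = **-5.17**, criterion not met.

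**5. Range and tipping points**

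The last column gives the mean annual change in missing subjects at which the all-treated bound reaches -5.

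| Missing of 22 | Observed-data bound | All-treated bound at -8 | Tipping value |
|---|---|---|---|
| 1 | -4.28 | -4.51 | -14.1 |
| 2 | -4.34 | -4.85 | -9.1 |
| 3 | -4.41 | -5.17 | -7.1 |
| 4 | -4.49 | -5.50 | -6.0 |
| 5 | -4.57 | -5.81 | -5.3 |

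Reversal at -8 starts at 3 of 22 (14%).

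**6. How much depends on having no FVC at all**

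Set the true all-subject mean at exactly -5, so that the nominal pass rate is 2.5%. If the missing subjects decline at -8 and contribute nothing, an observed-data analysis passes in 5.8% of simulated trials with 3 missing and 10.1% with 5 missing.

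Now let the same 3 or 5 subjects be tested up to Week 24, 48 or 72 and average each subject's own slope (assumed slope SD 4.5, measurement SD 4, same decline before and after withdrawal). The pass rate is then about 2% to 3%, close to nominal. A random-coefficient model gave 1.6% to 8.4%, with some inflation after early loss and little after later loss, but from only 250 replicates per setting. These runs hold decline constant through withdrawal, so they do not cover faster decline afterwards.

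**The case against.** Four points can be made against this, and most of them limit it.

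- **The governing document is missing.** A reader might infer that the plan contains no other missing-data sensitivity analysis. The supplied documents do not support that, because protocol 9.4 sends the missing-data rules to the main-study SAP. Naming observed data as the sensitivity analysis even suggests that the primary analysis handles missing values in some other way. This stands: the gap is shown for the supplied documents only.
- **OLE SAP section 5.3 is not the Week 104 rule.** It is tempting to read its no-imputation sentence as governing the primary criterion. It covers subjects dosed in the OLE, and protocol 7.1.4 bars those who withdraw before Week 104 from entering. The withdrawals at issue lie outside its population. This stands too.
- **Withdrawn subjects need not vanish.** Lung function is scheduled at Weeks 12, 24, 36, 48, 60, 72, 84 and 104 (protocol Appendices 1 to 3). One post-baseline FVC is enough for the FAS, and final testing is encouraged. Step 6 shows how far this shrinks the bias, so the table in step 5 is an upper range.
- **This is an exploratory Phase 2 study.** Its stated objective is to estimate efficacy, and protocol 9.5 calls it exploratory. That argues against a strict robustness gate. It does not argue against reporting a tipping point, because protocol 9.4.1 still declares success against a fixed bound.

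**Conclusion.** The point holds in a limited form. The sensitivity evaluation named in protocol 9.4 does not vary unobserved FVC in the unfavourable direction, and nothing supplied fills that gap. Agreement between it and the primary analysis would not show robustness to faster decline after withdrawal.

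The reversal from -4.41 to -5.17 requires at least 3 of 22 treated subjects with no usable FVC, declining 8% per year, against observed subjects at -2 with SD 5. With 1 or 2 such subjects the conclusion is unchanged, and partial follow-up reduces the bias greatly.

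A reader might go further and infer that the observed-data check would falsely confirm success. The documents do not establish that. They give no dropout rate, the primary missing-data method is not visible, and the calculation compares an observed mean with complete data without modelling the primary analysis. It is the primary analysis that decides success, and the weakness here lies in the reassurance drawn from the check.

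**What to change.** In protocol 9.4 and the main-study SAP (not OLE SAP section 5.3), specify for the Week 104 primary endpoint a delta-adjusted tipping-point analysis in all treated subjects, including those with no post-baseline FVC. Impute ppFVC after the last observed value, worsen the post-withdrawal annual decline in steps, and report the decline at which the lower 95% bound reaches -5%. Show 8.0% per year as one reference scenario, not as a pass/fail gate: it is a natural-history median, and using it for everyone assumes no treatment effect after withdrawal. Tabulate withdrawals by reason and last FVC so that readers can judge whether the tipping value is plausible. Keep the observed-data analysis as supportive. If version 1.0 of the main-study SAP already contains such an analysis, a cross-reference in section 9.4 is enough.

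The cost is wording and a little programming, with no new data. The addendum reports that database lock has been reached and an interim study report completed, so an analysis added after that point must be labelled post hoc. The downside is that a positive result may look less robust. If few subjects are missing, an extreme tipping value would strengthen it.

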### **9.4.1. Primary Endpoint**

The primary endpoint is the annual change from baseline to Week 104 in percent predicted FVC during treatment with pamrevlumab. The mean annual change in percent predicted FVC and the corresponding 2-sided 95% confidence interval will be presented. The primary efficacy endpoint will be met if the lower bound of 2-sided 95% confidence interval is greater than -5%.

### **9.4.2. Analyses of Other PFT Parameters**

Changes from baseline to Week 104 in other PFT parameters will be estimated similarly; details of missing data handling will be described in the statistical analysis plan (SAP).

### **9.4.3. Analysis of PUL Parameters, Pinch and Grip Strength, Brooke Scale**

Change from baseline to Week 104 in hand/arm function and strength will be analyzed. In order to evaluate overall effect, composite scores may be explored. Two-sided 95% confidence intervals will be presented.

### **9.4.4. Analysis of LVEF, Cardiac Fibrosis, and Muscle Fat and Fibrosis**

Changes from baseline in LVEF, cardiac fibrosis, and muscle fat and fibrosis will be summarized descriptively based on available data at Week 104.

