#### 4.1.2. Secondary Endpoints

The following are the secondary endpoints:

- Change from baseline to Week 104 in forced expiratory volume (FEV1), maximum inspiratory pressure (MIP), maximum expiratory pressure (MEP), peak expiratory flow (PEF), peak cough flow
- Change in LVEF from baseline to Week 104
- Change from baseline to Week 104 in Performance of Upper Limb (PUL) Score
- Change from baseline to Week 104 in grip strength, pinch strength, and Brooke scale for upper extremity
- Change from baseline to Week 104 in cardiac fibrosis score assessed by MRI
- Change from baseline to Week 104 in upper arm (bicep) muscle fat and fibrosis assessed by MRI

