#### **7.1.4. Early Withdrawal from Treatment and Safety Follow-up Period**

Subjects who prematurely discontinue the main study should be strongly encouraged to complete the final efficacy evaluations scheduled for Week 208/EOT as applicable, and the safety follow-up evaluations scheduled for the Week 210/EOS visit (4 weeks following the last dose).

Subjects who withdraw prior to week 104 will not be eligible to participate in the OLE.

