- g. Pulmonary function tests (PFTs): forced vital capacity, forced expiratory volume in 1 second, maximal inspiratory pressure, maximum expiratory pressure, peak expiratory flow rate, peak cough flow. PFTs will be performed during the screening period. PFTs will be repeated on Day 0 (start of dosing) or at any time up to and including the Week 2 visit. The results from both time points will be used to establish baseline values.
- h. See [Appendix 5](#) for pharmacokinetic/human antihuman antibody/connective tissue growth factor and Exploratory Sample collection details.
- i. Baseline muscle MRI may be conducted during the screening period or up to Week 4 dosing visit. Local safety labs are required prior to the MRIs, and must include hematocrit.

## APPENDIX 2. SCHEDULE OF ASSESSMENTS: WEEK 28 THROUGH WEEK 58

Assessment a	Treatment Period (Weeks)													
	28	30	32	34	36	38	40	42	44	46	48	50	52	54,56, 58
Clinical laboratory assessments b,i					X						X			
Vital Signs c	X	X	X	X	X	X	X	X	X	X	X	X	X	X
Weight/Height d					X						X			
Electrocardiogram												X		
Physical Examination e					X						X			
Muscle function tests f					X						X			
Pulmonary function tests g					X						X			
Cardiac MRI i													X	
Muscle MRI i													X	
Specialty labs h														X
Pamrevlumab infusion	X	X	X	X	X	X	X	X	X	X	X	X	X	X
Adverse Events & Concomitant Medications	X	X	X	X	X	X	X	X	X	X	X	X	X	X
PODCI Quality Outcome Questionnaire													X	

Abbreviations: MRI, magnetic resonance imaging; PODCI, Pediatrics Outcomes Data Collection Instrument

- See [Section 7](#) for details on approved windows, assessments and dosing.
- Safety labs: See [Section 7.2.7.1](#). Central labs are required at visits noted in this table.
- Vital signs (pulse, respiration, sitting blood pressure, and temperature) to be collected at every visit, and pre-infusion, within 15 minutes of infusion completion and within 15 minutes of completing the observation period.
- Weight and height (estimated from ulna length) to be measured at screening and approximately every 3 months thereafter.
- Physical exam to include assessment of subject's ventilation use. A complete exam is required at Week 48. Other exams may be disease specific or problem oriented.
- Muscle function tests: Brooke Scale, Performance of Upper Limb, Pinch Strength Test, and Grip Test.

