9.2.3.1. Analysis Method

The observed and change from baseline in the above efficacy endpoints each will be summarized by analysis visit and analyzed using MMRM with visit, baseline, and age with appropriate covariance matrix for the within subject covariance over time.

If the algorithm for unstructured covariance pattern does not converge, the following covariance structures will be tested in sequence until the model converges: heterogeneous Toeplitz, homogeneous Toeplitz, first-order autoregressive, compound symmetry, and variance component. The sandwich estimator will be used if there is convergence issue. If the model does not converge for all covariance structures listed above, some least significant factors or interaction terms ($p>0.05$) can be excluded from the model to achieve convergence. The revised model with fewer factors or interaction terms will be tested using the same sequence as specified above.

9.2.3.2. Handling of Intercurrent Events:

Treatment discontinuation (such as: due to AEs, Lost to Follow-Up, Withdrawal by subject, Physician Decision, Protocol Deviations, etc.): treatment policy: the occurrence of the intercurrent event is irrelevant. All observed values will be used regardless of whether the inter-current event occurs.

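### The protocol's Week 104 summary of the MRI endpoints gives no role to the Week 52 scans of subjects who have no Week 104 scan, so the mean change can look too favourable if loss follows poor scans

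*Protocol*

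**What the plan says.** Protocol section 4.1.2 lists the MRI measures as secondary endpoints, among them "Change in LVEF from baseline to Week 104" and "Change from baseline to Week 104 in upper arm (bicep) muscle fat and fibrosis assessed by MRI". Section 9.4.4 sets their analysis: "Changes from baseline in LVEF, cardiac fibrosis, and muscle fat and fibrosis will be summarized descriptively based on available data at Week 104". It names no model, no confidence interval and no use of an earlier scan.

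The surrounding text differs in three ways:

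- Section 9.4 places efficacy analyses in the FAS, leaves missing-data rules to the SAP, and adds: "Analyses based on observed data will be performed for sensitivity evaluation".
- Section 9.4.2 also defers missing data to the SAP, and section 9.4.3 promises 95% confidence intervals. Section 9.4.4 does neither.
- Section 9.4.5 summarises the PODCI at each assessment time. Section 9.4.4 names Week 104 only.

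Cardiac and muscle MRI are scheduled once in the protocol's "APPENDIX 2. SCHEDULE OF ASSESSMENTS: WEEK 28 THROUGH WEEK 58", in the column that reads as Week 52, and again at Week 104 in Appendix 3. On withdrawal, section 7.1.4 says: "Subjects who prematurely discontinue the main study should be strongly encouraged to complete the final efficacy evaluations scheduled for Week 208/EOT". In Appendix 4 that visit includes both MRIs, but no text says whether such a scan counts as Week 104.

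The supplied OLE SAP (section 9.2.3) does model LVEF, LGE fibrosis and circumferential strain over time, "analyzed using MMRM with visit, baseline, and age with appropriate covariance matrix for the within subject covariance over time".

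**The concern.** The reasons a Week 104 scan may be missing in this disease include cardiac or respiratory decline, death, and no longer being able to undergo MRI. These are plausibly linked to what the scans measure: protocol section 2.2 describes cardiac dysfunction as a leading cause of morbidity and mortality, and ties myocardial fibrosis to falling LVEF. A mean over subjects still scanned at Week 104 then describes a selected group. The trial has one arm, so no control group undergoes the same selection, and the MRI changes can only be judged against an expected decline. If the selection favours subjects who were doing well, the drug looks better than it should, while Week 52 scans that carry part of the missing information stay out of the mean.

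**Working it through.** **The plan's own figure.** The documents give no sample size, SD, dropout rate or effect for the MRI endpoints. The only planning figure is for FVC in section 9.1: n = 22 from a difference of 3, SD 5, two-sided 0.05 and 80% power. The normal approximation gives (5 × (1.960 + 0.842) / 3)² = 21.8, so 22. I use only n = 22 from it.

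**Assumptions (none is in the documents).**
- Loss between Weeks 52 and 104: q = 10-20%.
- Odds of loss multiplied by OR = 2-3 for each SD of worse Week 52 change.
- Correlation between the Week 52 and Week 104 changes: ρ = 0.5-0.7.
- Changes bivariate normal, in SD units, oriented so that higher is better.

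**Formula.** Let z be the standardised Week 52 change and P(loss | z) = 1 / (1 + exp(−(a − b·z))), with b = ln(OR) and a chosen so that average loss equals q. Then

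bias of the Week 104 available-case mean = ρ × E[z | not lost].

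Numerical integration gives:

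| q | OR | a | E[z, not lost] | bias, ρ = 0.5 | bias, ρ = 0.7 |
|---|---|---|---|---|---|
| 10% | 2 | −2.381 | 0.066 | 0.033 | 0.046 |
| 10% | 3 | −2.633 | 0.098 | 0.049 | 0.068 |
| 15% | 2 | −1.893 | 0.098 | 0.049 | 0.068 |
| 20% | 2 | −1.521 | 0.129 | 0.064 | 0.090 |
| 20% | 3 | −1.697 | 0.186 | 0.093 | 0.130 |

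The range is therefore 0.033 to 0.130 SD.

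**Where it vanishes, reverses or grows.**
- At 5% loss, OR 3 and ρ = 0.7, the bias is 0.036 SD.
- If loss is unrelated to the scan, it is zero.
- If better subjects leave, it has the same size and opposite sign. In simulation at n = 22, q = 20%, ρ = 0.7 and a log-odds slope of 1 per SD, it is +0.122 when worse subjects leave and −0.120 when better subjects leave.
- Extreme case: the worst q at Week 52 all leave. The bias is then ρ × φ(z_q) / (1 − q), where φ is the standard normal density and z_q its q-th quantile. At q = 20% and ρ = 0.7 this is 0.7 × 0.280 / 0.80 = 0.245 SD.

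**Against sampling error.** With 22 × 0.9 = 19.8 subjects scanned, the standard error is 1/√19.8 = 0.225 SD. With 22 × 0.8 = 17.6 it is 1/√17.6 = 0.238 SD. The biases in the table run from 0.033 / 0.225 = 0.15 to 0.130 / 0.238 = 0.55 of one standard error.

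**What a repeated-measures estimate does.** In the same simulations, a likelihood estimate that keeps the Week 52 scans has bias within 0.003 SD throughout. In the q = 20%, ρ = 0.7 case with worse subjects leaving, the SD of the estimate is 0.234, against 0.236 for the available-case mean. Loss was generated from the Week 52 change alone, so missing-at-random holds by construction. This shows that the method works under that condition, not that the condition holds here.

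**Does other supplied text close the gap?** The OLE models run on SAF-OLE (OLE SAP section 5.2.1). Subjects who withdraw before Week 104 cannot enter the OLE (protocol section 7.1.4), so those models never include them, and they omit muscle fat and fibrosis. The SAP addendum does not mention missing MRI data.

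**The case against.** The strongest objection is that the governing document is unseen. The protocol synopsis sends the final analysis of primary and secondary endpoints to the SAP, and section 9.4 sends the missing-data rules there. Main-study SAP version 1.0, cited in the addendum, was not supplied. The addendum's remark that some annual-change estimates for secondary endpoints are dropped for data or model limitations suggests that it held model-based secondary analyses. This stands: a reader might infer from section 9.4.4 that the available-case summary is the only MRI analysis, and the documents do not establish that.

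A reader might also infer that subjects lost after Week 52 vanish from the report. They do not. Section 9.3.1 promises listings for all ITT/Safety subjects and descriptive summaries of all parameters, and sections 4.2 and 7.1.4 seek a final assessment at withdrawal. The gap concerns the Week 104 mean only.

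The endpoints are descriptive, with no test or success rule, and under the main assumptions the bias stays below about 0.55 of one standard error. That also stands and limits the importance of the point.

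Finally, MMRM is not a full answer. It does not correct for decline or death after Week 52 that the scan does not predict, and a subject lost before Week 52 without a post-baseline scan adds nothing. Nor does the OLE SAP supply ready code: its Appendix 2 shows random-coefficient models only.

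**Conclusion.** The point holds in a conditional form. Section 9.4.4 as written leaves Week 52 scans out of the Week 104 mean for subjects without a Week 104 scan, and no supplied document repairs this. Under the assumed 10-20% loss, odds ratio 2-3 and correlation 0.5-0.7, the mean is too favourable by about 0.03 to 0.13 SD. The tempting stronger conclusion, that the MRI results are in fact biased towards the drug, is not supported: the documents give no dropout rate and no link between scan result and withdrawal, and both size and sign depend on them. The primary FVC conclusion is not touched. This is a low-cost improvement to secondary endpoints, held with low confidence because SAP version 1.0 has not been seen.

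**What to change.** First check SAP version 1.0. If it already covers this, align section 9.4.4 with it. If not:

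1. Estimate the Week 104 change in LVEF, cardiac fibrosis score, and muscle fat and fibrosis in the FAS by MMRM on the Week 52 and Week 104 changes, with visit, baseline value and age, unstructured covariance, Kenward-Roger degrees of freedom and a 95% confidence interval.
2. Keep the observed Week 104 summary as the sensitivity analysis, in line with section 9.4.
3. Report how many subjects have a Week 52 but no Week 104 scan, with their Week 52 change.
4. State how early-termination scans are assigned to visits.

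The addendum records that database lock has occurred and an interim CSR is complete. The model must therefore be labelled supplementary unless SAP version 1.0 specifies it. It can still be reported, because the OLE data are yet to be summarised in the study report (OLE SAP section 1.2).

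The cost is one model per MRI endpoint, with code to be written, and a short table. The statistical price is reliance on missing-at-random given the Week 52 scan, which should be stated beside the results.
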